#### 4.1.2 General Concomitant Medication and Supportive Care Guidelines

Participants will be required to take antibiotics for prevention of *Pneumocystis jiroveci* infection throughout the duration of the clinical trial. Participants will be instructed to take 1 tablet of Bactrim DS every Monday, Wednesday and Friday while taking idelalisib. If there is a concern for allergy or other adverse reaction to Bactrim DS in the opinion of the treating investigator, atovaquone 1500 mg daily may be prescribed instead.

Participants will be instructed not to take any additional medications (including over-the-counter products) during the course of the study without prior consultation with the investigator. At each visit, the investigator will ask the participant about any new medications he/she is or has taken after the start of the study drug.

Anti-emetics are permitted if clinically indicated. Standard supportive care medications are permitted. All concomitant medications/significant non-drug therapies taken  $\leq$  30 days prior to start and after start of study drug, including physical therapy and blood transfusions, should be recorded. The following restrictions apply during the entire duration of the study:

- No other investigational therapy should be given to participants.
- No anticancer agents other than the study medication should be given to participants. If such agents are required for a patient then the patient must first be withdrawn from the study.
- Growth factors (e.g. G-CSF, erythropoietin, platelet growth factors etc.) are not to be administered prophylactically but may be prescribed at the discretion of the treating physician for treatment related hematologic events in accordance with ASCO guidelines.
- Concurrent administration of idelalisib and strong CYP3A4/5 inhibitors (such as clarithromycin, ketoconazole, itraconazole, and ritonavir) and inducers (such as rifampin and rifabutin) should be avoided. Alternatives should be sought if possible. Provided there is no alternative treatment available, the Principal Investigator should be consulted, and treatment should be administered with caution; patients should be closely monitored for potential toxicities with temporary interruption of idelalisib. Examples are provided in Table 4-1.
- Concurrent administration of idelalisib and moderate CYP3A4/5 inhibitors (such as erythromycin, fluconazole, calcium channel blockers, benzodiazepines) and moderate CYP3A4/5 inducers (such as carbamazepine and phenobarbital) should also be avoided if possible, or after consulting with the Principal Investigator, used with caution with increased frequency of safety monitoring and temporary interruption of idelalisib
- Competitive inhibition could occur when idelalisib is combined with drugs, which are also CYP3A4/5 substrates; and therefore should be avoided.
- Co-administration with substrates, inducers, or inhibitors of P-glycoprotein should be avoided, if possible, or used with caution with increased frequency of safety monitoring and temporary interruption of idelalisib.
- Grapefruit and grapefruit juice affect cytochrome P450 and P-glycoprotein activity and should therefore be avoided.

- In addition, patients should avoid Seville oranges and star fruit, as well as the juice of these fruits, which are potent CYP3A4-inhibitors.
- No green tea or foods/supplements containing green tea or extract.
- No chronic treatment with systemic steroids (at dosages equivalent to prednisone >20 mg/day) or other immunosuppressive agents. Topical or inhaled corticosteroids are allowed.

Inhibitors of CYP3A4/5 are defined as follows. A comprehensive list of inhibitors can be found at the following website: <http://medicine.iupui.edu/clinpharm/ddis/table.aspx>. The general categorization into strong, moderate, and weak inhibitors according to the website is displayed below:

- A strong inhibitor is one that causes a >5-fold increase in plasma AUC values or >80% decrease in clearance. Strong inhibitors are capitalized in the list below.
- A moderate inhibitor is one that causes a >2-fold increase in plasma AUC values or 50-80% decrease in clearance.
- A weak inhibitor is one that causes a >1.25-fold but <2-fold increase in plasma AUC values or 20-50% decrease in clearance.

**Table 4-1 Inhibitors and Inducers of CYP3A4/5**

Inhibitors of CYP3A4/5	Inducers of CYP3A4/5

Strong inhibitors:
 
INDINAVIR NELFINAVIR RITONAVIR CLARITHROMYCIN ITRACONAZOLE KETOCONAZOLE NEFAZODONE SAQUINAVIR TELITHROMYCIN
 
Moderate inhibitors:
 
Aprepitant erythromycin Diltiazem Fluconazole grapefruit juice Seville orange juice Verapamil
 
Weak inhibitors:
 
Cimetidine
 
All other inhibitors:
 
Amiodarone NOT azithromycin chloramphenicol Boceprevir ciprofloxacin Delavirdine diethyl-dithiocarbamate fluvoxamine Gestodene Imatinib Mibepradil mifepristone Norfloxacin norfluoxetine star fruit Telaprevir troleandomycin voriconazole
	
Carbamazepine Efavirenz Nevirapine Barbiturates Glucocorticoids Modafinil Oxcarbazepine Phenobarbital Phenytoin Pioglitazone Rifabutin Rifampin St. John's Wort Troglitazone

Source: <http://medicine.iupui.edu/clinpharm/ddis/table.aspx>

#### 4.1.3 Duration of Therapy

Duration of therapy will depend on individual response, evidence of disease progression and tolerance. In the absence of treatment delays due to adverse events, treatment may continue until one of the following criteria applies:

- Disease progression (including initiation of new therapy) or death
- Dose delay of >28 days for toxicity
- Intercurrent illness that prevents further administration of treatment
- Unacceptable toxicity or adverse event(s)
- Participant demonstrates an inability or unwillingness to comply with the oral medication regimen and/or documentation requirements
- Participant decides to withdraw from the study
- General or specific changes in the participant's condition render the participant unacceptable for further treatment in the opinion of the treating investigator.

**Participants who meet criteria for disease progression but are deemed by the investigator to be clinically benefiting from idelalisib will be permitted to continue on protocol at the Principal Investigator's discretion. Clinical benefit is determined by considering clinical data, such as overall participant performance and disposition, CBC, and when necessary, bone marrow biopsy results and CT scans.**

#### 4.1.4 Duration of Participation

Participants will continue to take Idelalisib per-protocol until disease progression or unacceptable adverse event. Study visits will occur two weeks after starting Idelalisib, then monthly from the start of Idelalisib for three months, followed by every three months from the start of Idelalisib thereafter until disease progression or the start of another line of therapy, whichever occurs first. For patients who have responded but come off Idelalisib for reasons other than progression, they will be followed every 6 months until progression or another line of therapy. An end of study visit will take place 30 days following the last dose of Idelalisib. The duration for individuals, and duration of the study, are dependent upon disease response. We anticipate no more than 2 years duration for individual subjects. We anticipate the study will remain active for a total of 4 years including enrollment, treatment, follow-up and data analysis.

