### 1.1.7 Secondary Objectives:

- To assess progression free survival (defined as the interval from the first documentation of CR, VGPR or PR to the earlier of the first documentation of disease progression)
- To determine organ response (defined as improvement of involved organ function i.e. eGFR for kidneys, EF for heart etc.)
- To assess the safety and tolerability of idelalisib
- To measure impact on QOL of life using SF-36 assessment tool.

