Neutropenia	ANC 1.0 to <1.5 Gi/L	ANC 0.5 to <1.0 Gi/L	ANC <0.5 Gi/L
	Maintain Idelalisib dose.	Maintain Idelalisib dose. Monitor ANC at least weekly.	Interrupt Idelalisib. Monitor ANC at least weekly until ANC $\geq$ 0.5 Gi/L, then may resume Idelalisib at 100 mg BID (or if taking 150mg BID, decrease to 100mg).
Thrombocytopenia	Platelets 50 to <75 Gi/L	Platelets 25 to <50 Gi/L	Platelets <25 Gi/L
	Maintain Idelalisib dose.	Maintain Idelalisib dose. Monitor platelet counts at least weekly.	Interrupt Idelalisib. Monitor platelet count at least weekly. May resume Idelalisib at 100 mg BID (or if taking 150mg BID, decrease to 100mg) when platelets $\geq$ 25 Gi/L.

Abbreviations: ALT, alanine aminotransferase; AST, aspartate aminotransferase; ANC, absolute neutrophil count; BID, twice daily; ULN, upper limit of normal

Dose re-escalations will not be permitted once dose reduced to next lower dose level. If a participant requires a dose delay of 28 days or more, then the participant must be discontinued from the study.

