## 7.0 STUDY CALENDAR

	At enrollment	Every 2 weeks for 3-6 months after starting Idelalisib 	One and two months after starting Idelalisib 	Monthly while taking Idelalisib	Every three Months 	End of Study Treatment Visit 
PHYSICAL						
History & Physical Exam	X				X	X
Height & Weight	X					
ECOG Performance Status (see Appendix A)	X		X		X	X
Adverse Event Monitoring			X		X	X
SF-36 (QOL)	X		X		X	
LABORATORY-Serum						
Complete Blood Count with Differential	X	X 	X		X	X
Beta-HCG 	X					
Chemistry including: BUN, creatinine, glucose, sodium, potassium, chloride, bicarb, cholesterol, CK, calcium, total protein, LDH, magnesium, phosphorous, triglycerides, uric acid, TSH, amylase	X		X		X	X
BUN / Serum Creatinine	X		X		X	X
Hepatic Function Testing: ALT/AST, Bilirubin, Albumin, Alkaline Phosphatase	X	X 	X		X	X
β-2 Microglobulin / C-reactive protein	X		X		X	
Cardiac enzymes: BNP/ Troponin I	X		X		X	
Serum free light chain assay	X		X		X	
SPEP, SIFE, Immunoglobulins	X		X		X	
Vitamin B12, folate, ESR, retic %	X		X			
Coagulation profile: PTT, INR, D-dimer, Factor X	X		X		X	
Hepatitis Serologies: Hep B Surface Antigen, Hep B Core antibody, Hep C Antibody	X					
HIV antibody- 1+2	X					
CMV PCR	X			X		
1, 3 β-D-glucan	X			X		
LABORATORY-Urine						
Urinalysis	X				X	
24 hour urine: total protein, creatinine, kappa, and lambda	X				Every 6 months	
UPEP / UIFE / TV	X				X	
PATHOLOGY						
BM biopsy w/ MYD88 and CXCR4 WHIM analysis 	X					
FISH for t(11;14)	X					
Fat aspirate (if not previously done)	X					
X-RAYS AND SCANS						
ECG / CXR	X					
Echocardiogram	X				Every 6 months	
PFTs	X					

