For women of childbearing potential only: Serum pregnancy test is required at screening.If bone marrow biopsy and aspiration must have been repeated following any previous therapy > 1 cycle.These visits including physical exam and blood work may be performed by local physician and confirmed by telephone contact if patient unable to return for week 2 visit or monthly visits on months 1 and 2.CBC with differential should be monitored every 2 weeks for the first 6 months of treatmentHepatic function tests should be checked every 2 weeks for the first 3 months of treatmentWhile on study drug or until disease progression or start of another therapy.30 days following last dose (+/-) 7 days.

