#### 8.5 Progression-Free Survival

Progression-Free Survival (PFS) is defined as the duration of time from start of treatment to time of objective disease progression (including initiation of new therapy or death). Follow-up will continue until disease progression, which we anticipate to be no more than 2 years.

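### The protocol contradicts itself on disease follow-up after idelalisib is stopped; on one reading, non-responders who stop for toxicity are censored early from PFS

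*Combined protocol and SAP*

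**What the plan says.** All references are to the combined protocol and SAP.

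**Text that follows everyone**
- Section 8.5 measures PFS from the start of treatment: "defined as the duration of time from start of treatment to time of objective disease progression (including initiation of new therapy or death". It adds: "Follow-up will continue until disease progression, which we anticipate to be no more than 2 years". Neither sentence mentions response or being on drug.
- The general visit sentence in section 4.1.4 has visits "followed by every three months from the start of Idelalisib thereafter until disease progression or the start of another line of therapy".
- Footnote 6 to the Study Calendar (section 7.0), on the three-monthly column, reads "While on study drug or until disease progression or start of another therapy".

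**Text that does not**
- Section 4.1.4, for patients who have stopped drug: "For patients who have responded but come off Idelalisib for reasons other than progression, they will be followed every 6 months until progression". No matching sentence covers non-responders. An end-of-study visit is set 30 days after the last dose.
- Section 5: "If a participant requires a dose delay of 28 days or more, then the participant must be discontinued from the study". Section 5.1.1 repeats the rule. It also says that patients stopped for toxicity are followed until the event resolves or falls to grade 1, and does not mention disease status.
- In the Study Calendar, the row "Serum free light chain assay" is marked at enrollment, at months 1 and 2 and every three months, but not at the End of Study Treatment Visit. The rows for SPEP/SIFE/immunoglobulins and UPEP/UIFE are also blank there.

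**Related text**
- Section 1.1.7 gives a different PFS, "defined as the interval from the first documentation of CR, VGPR or PR to the earlier of the first documentation of disease progression".
- Section 12 has no censoring rule for PFS.

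**The concern.** Whether a patient is still observed for PFS should not depend on whether that patient responded or why the drug was stopped. Under the narrower wording it depends on both. A patient with stable disease who stops for toxicity has no clearly written disease follow-up, and the one visit that is certain to take place cannot show hematologic progression.

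Such patients are likely to exist. Section 2.1.5 gives a median onset of hepatotoxicity of 28 days, and section 2.1.8 gives a median time to response of 2 months in study 101-09. Some toxicity stops will therefore come before a response could be established. These patients may also soon start another therapy. Section 8.5 counts that as an event, but it would go unrecorded once they are off study. If they progress sooner than the patients still under observation, censoring them is informative and the PFS curve is too high. Assessments that were never made cannot be recovered at analysis.

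**Working it through.** **1. The plan's own figures.** The documents give no sample size, event count or power for PFS, so there is nothing to reproduce for this endpoint. The only design figure is the two-stage rule for response rate in section 12.2 (9 + 9 = 18 patients, success with at least 3 responses). Off-drug PFS follow-up does not enter it.

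**2. Do the passages fit together?** Suppose the general visit sentence and footnote 6 govern everyone. Then an off-drug non-responder is seen every 3 months and an off-drug responder every 6, and anyone discontinued from the study under sections 5 and 5.1.1 must still attend. Suppose instead that the responder sentence governs off-drug patients. Then section 8.5 is not met for non-responders. Neither reading satisfies all the passages.

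**3. Is the calendar gap real?** Blood count, chemistry and hepatic function are marked in the End of Study Treatment column, so that column is in use. Section 8.2 defines progression by serum M-protein, urine M-protein or free light chain. None of the three is marked there.

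**4. How many patients?** Expected number = N × (rate of stopping for adverse events) × (1 − response rate), taking stopping as independent of response.
- N = 18 and response rate 25% (p1), from section 12.2.
- Stopping rates from sections 2.1.5 to 2.1.8 of the background, all in other diseases: 12% (101-02/101-99), 15% (101-09), and 2 of 11 = 18% (101-10, where 1 subject is 9%, so 11 were treated).

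| Stopping rate | Expected patients | Chance of at least one |
|---|---|---|
| 12% | 18 × 0.12 × 0.75 = 1.6 | 1 − (1 − 0.09)^18 = 82% |
| 15% | 18 × 0.15 × 0.75 = 2.0 | 1 − (1 − 0.1125)^18 = 88% |
| 2/11 | 18 × 0.182 × 0.75 = 2.5 | 1 − (1 − 0.136)^18 = 93% |

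Over N of 15 to 18, stopping rates of 12 to 30% (30% is an assumption) and response rates of 5 to 57%, the range is 0.8 to 5.1 patients.

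**5. Effect on median PFS.** This was simulated. Exponential PFS with a median of 11 months is borrowed from 101-09, which was indolent lymphoma at a different dose. Stops fall at months 1 to 4, responders are followed, and non-responders are censored at stopping. The off-drug hazard ratio is an assumption that the documents do not inform.

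| Stopping | Off-drug hazard ratio | True median | Estimated median | Excess |
|---|---|---|---|---|
| 15% | 1 | 11.0 | 11.0 | 0 |
| 15% | 2 | 10.1 | 10.7 | 0.6 |
| 15% | 3 | 9.5 | 10.5 | 1.0 |
| 30% (assumed) | 2 | 9.2 | 10.4 | 1.2 |
| 30% (assumed) | 3 | 8.3 | 10.1 | 1.8 |

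Censoring one month after stopping, near the 30-day visit, leaves 0.5 to 0.8 months at 15% stopping.

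A second model makes stopping unrelated to progression risk but gives non-responders a shorter PFS than responders (assumed medians 3 to 5.5 against 12.5 months). At 12 to 15% stopping the excess is then about 0.04 to 0.2 months in the median and 0.6 to 1.2 percentage points in 12-month PFS.

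**The case against.** The strongest reply is that the plan does follow everyone. Section 8.5, the general visit sentence and footnote 6 all run to progression without naming responders, and the 6-month rule can be taken as a relaxation for responders only. That reading is available, so a reader should not infer that non-responders are certain to be lost. It still does not fit with discontinuation from the study, and sites would have to guess.

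Other stronger readings also fail:
- **All toxicity stoppers leave the study.** The mandatory rule covers only dose delays of 28 days or more. The other stopping rows in section 5 end the drug without ending study participation. Section 5.1.1 lists adverse events as a reason participation may end, and lets some patients continue at the Principal Investigator's discretion.
- **A patient stopping at week 6 has only the month-1 light-chain value.** The month-2 tests are timed from the start of drug and may be done locally. They fall before an end visit at about week 10 (42 + 30 = 72 days).
- **The primary endpoint is biased upward.** Section 12.4 keeps every eligible enrolled patient in the response analysis, so a response missed at the end visit would lower the rate.
- **The 6-month interval for off-drug responders is a serious second bias.** It adds about 1.5 months of average detection delay (3.0 − 1.5), but in only 18 × 0.25 × 0.12 to 0.18 = 0.5 to 0.8 expected patients.

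It is also fair that PFS is secondary with no test or power claim, and that the sampling standard deviation of a median from 18 exponential patients is about 3.7 months, well above the bias. Under the PFS definition in section 1.1.7, non-responders have no start date and a responder-only rule is coherent. That does not remove the problem, because it shows that the two definitions also have to be reconciled.

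**Conclusion.** The point holds as an internal contradiction with a possible, modest effect on a secondary endpoint. The documents do not settle who is followed for disease after stopping idelalisib, and the end-of-treatment visit lacks the tests that define hematologic progression.

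If the responder-only and off-study wording is applied, about 1.6 to 2.5 of 18 patients would be censored early from PFS as defined in section 8.5. PFS is overstated only if those patients would progress sooner than the patients still followed. At 15% stopping the excess is about 0.6 to 1.0 months in the median for an assumed off-drug hazard ratio of 2 to 3. It is zero at a ratio of 1 with a common hazard, and 0.2 months or less if the only difference is that non-responders progress sooner than responders. The stopping rates are from other diseases and the hazard ratios are assumptions. The primary response-rate test is essentially unaffected.

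**What to change.** 1. In section 4.1.4, extend off-drug follow-up to all patients who stop for reasons other than progression, on one common schedule that agrees with footnote 6. The choice of interval is secondary.
2. In sections 5 and 5.1.1, separate leaving treatment from leaving follow-up, so that patients who stop drug are still followed for response, progression, new therapy and death.
3. Add serum free light chains, SPEP/SIFE/immunoglobulins and UPEP/UIFE to the End of Study Treatment column for patients without documented progression, with local draws allowed.
4. Reconcile the PFS definitions in sections 1.1.7 and 8.5, and state the censoring rule in section 12.

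No treatment-stopping rule and no sample size changes. The cost is protocol wording plus a few blood and urine tests and follow-up contacts in about 2 to 3 patients (18 × 0.12 to 0.18 = 2.2 to 3.3 stopping for adverse events, responders included).

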### 5. EXPECTED TOXICITIES AND DOSING DELAYS/DOSE MODIFICATIONS

If possible, symptoms should be managed symptomatically. In the case of toxicity, appropriate medical treatment should be used (including anti-emetics, anti-diarrheals, etc.). All adverse events experienced by participants will be collected from the time of the first dose of study treatment, through the study and until the final study visit. Participants continuing to experience toxicity at the off study visit may be contacted for additional assessments until the toxicity has resolved or is deemed irreversible.

For patients who are unable to tolerate the protocol-specified dosing schedule, dose adjustments are permitted. If administration of idelalisib must be interrupted because of unacceptable toxicity, drug dosing will be interrupted or modified according to the manufacturer's guidelines seen below. Toxicities requiring dose modification that recur upon restarting drug should be discussed with the principal investigator.

Dose Modifications for Toxicities Due to Idelalisib			
Pneumonitis: Discontinue Idelalisib in patients with any severity of symptomatic pneumonitis			
Intestinal Perforation: Discontinue Idelalisib			
Positive CMV PCR: Consider confirmation (at investigator discretion) Discontinue Idelalisib			
ALT/AST	>3-5 x ULN	>5-10 x ULN	>10 x ULN
	Maintain Idelalisib dose. Monitor at least weekly until <1 x ULN.	Withhold Idelalisib. Monitor at least weekly until ALT/AST are <1 x ULN, then may resume Idelalisib at 100 mg BID (or if taking 150mg BID, decrease to 100mg).	Discontinue Idelalisib permanently.

Bilirubin	>1.5-3 x ULN	>3-10 x ULN	>10 x ULN
	Maintain Idelalisib dose. Monitor at least weekly until <1 x ULN.	Withhold Idelalisib. Monitor at least weekly until bilirubin is <1 x ULN, then may resume Idelalisib at 100 mg BID (or if taking 150mg BID, decrease to 100mg).	Discontinue Idelalisib permanently.
Diarrhea	Moderate diarrhea (increase of 4-6 stools/day over baseline)	Severe diarrhea or Hospitalization (increase of 7 or more stools/day over baseline)	Life-threatening diarrhea
	Maintain Idelalisib dose. Monitor at least weekly until resolved.	Withhold Idelalisib. Monitor at least weekly until resolved, then may resume Idelalisib at 100 mg BID (or if taking 150mg BID, decrease to 100mg).	Discontinue Idelalisib permanently.
Neutropenia	ANC 1.0 to <1.5 Gi/L	ANC 0.5 to <1.0 Gi/L	ANC <0.5 Gi/L
	Maintain Idelalisib dose.	Maintain Idelalisib dose. Monitor ANC at least weekly.	Interrupt Idelalisib. Monitor ANC at least weekly until ANC $\geq$ 0.5 Gi/L, then may resume Idelalisib at 100 mg BID (or if taking 150mg BID, decrease to 100mg).
Thrombocytopenia	Platelets 50 to <75 Gi/L	Platelets 25 to <50 Gi/L	Platelets <25 Gi/L
	Maintain Idelalisib dose.	Maintain Idelalisib dose. Monitor platelet counts at least weekly.	Interrupt Idelalisib. Monitor platelet count at least weekly. May resume Idelalisib at 100 mg BID (or if taking 150mg BID, decrease to 100mg) when platelets $\geq$ 25 Gi/L.

Abbreviations: ALT, alanine aminotransferase; AST, aspartate aminotransferase; ANC, absolute neutrophil count; BID, twice daily; ULN, upper limit of normal

Dose re-escalations will not be permitted once dose reduced to next lower dose level. If a participant requires a dose delay of 28 days or more, then the participant must be discontinued from the study.

